3.2 Premature Discontinuation

If a subject chooses to discontinue treatment during the first treatment phase, he/she has the possibility either to withdraw from the study, or to continue the second phase of the study after a 2 week washout period.

Subjects will be withdrawn if they undergo a major surgery during the study period (any surgery that requires 2 or more days of hospitalization).

Subjects will be withdrawn from the study if during the study period they are placed on chemotherapy regimen that includes a taxane, a platinum compound or a vinca alkaloid.

Subjects will be withdrawn from the study if they require an increase in their other analgesic drugs, including chronic around-the-clock opioid dose; or need more than 4 PRN daily doses of a short-acting opioid.

Subjects will be withdrawn from the study in case of any of the following adverse events:

- Angioedema
- Hypersensitivity
- Suicidal behavior or ideation
- Peripheral edema in patients with New York Heart Association (NYHA) Class III or IV heart failure (in non-cardiac patients the peripheral edema due to pregabalin has not been associated with cardiovascular complications).

Subjects will be withdrawn if they experience any Grade 3 or higher adverse effect, if the investigator decides that discontinuation is in the best interest of the subject, or the subject requests withdrawal from the study.

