2.4.3 Study Period

[figure not shown]
The cross-over study design and the treatment plan are illustrated in Figure 1. Pregabalin (or matching placebo) will be administered for four weeks in each period. The target dose will be increased from 75mg BID to 300mg BID within 7 days (per schedule in Fig. 1), and continued for an additional 22 days.

In case of any grade 2 adverse events (Common Terminology Criteria for Adverse Events – CTCAE version 4.0), the dose will be reduced to the last dose prior to dose increase (i.e. to 150mg BID from 300mg BID; to 75mg BID from 150mg BID). If the adverse effect diminishes to \leq Grade 1, one attempt to dose escalate will be allowed after 3 additional days. If the dose escalation is not tolerated (i.e. recurrent grade 2 adverse event), the treatment will be continued at the previous (lower) dose until day 28. Any CTCAE \geq grade 3 will trigger subject withdrawal from the study.

At the end of treatment sequence, the dose will be tapered over 3 days (e.g., 150mg BID for 2 days, then 75 mg BID for 1 additional day) followed by 10 days of study drug-free washout (end of week 6). In subjects with CrCL 30-60 mL/min, the target (maximum) dose will be 300mg/day. In these subjects the dose will be tapered over 3 days of 75mg BID dosing. If subject's highest tolerable maintenance dose was 75mg BID, the taper schedule will be 75mg QD over 3 days.

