The subjects will return on day 28 ± 2 days [prior to washout period] for Visit 2 to turn in the 4 questionnaires which were completed on day 28 (week 4a), sensory mapping, PK blood sample and a blood sample for renal and hepatic function tests will be obtained. After the washout period (end of week 6), the subjects will return to Washington University Medical Center for Visit 3, prior to second treatment sequence. The subjects will undergo QST and CPM procedures (Fig. 1), and complete the appropriate questionnaires (SPI, NPSI, BPI, DAPOS). Thereafter, the second 4-week treatment sequence will be scheduled for weeks 7-10, according to the same titration schedule as sequence 1. Three day dose tapering-down will be practiced at the end of second treatment sequence in the same manner as was performed for the first treatment. The subjects will return for the final assessment visit [Visit 4] approximately 3 days after end of week 10 (end of 3-day taper). Safety and efficacy data, a PK blood sample and a blood sample for renal and hepatic function tests will be obtained, turn in 4 questionnaires which were completed on day 28 (week 4b), sensory mapping, and the optional skin biopsy in subjects who agreed, will be obtained at Visit 4.

Figure 1.

Legend: BPI – brief pain inventory; NPSI – neuropathic pain symptom inventory; DAPOS – depression, anxiety and positive outlook scale; SPI – sleep problem index; QST – quantitative sensory testing; CPM – conditioned pain modulation. Tx – treatment.

Rescue Analgesia

Study subjects will be allowed to take oral acetaminophen (paracetamol) as rescue analgesic at a dose of 1 gram up to 4 times/day. FDA-approved 500mg acetaminophen tablets will be purchased and provided by the investigators. If the patient has been receiving PRN short-acting opioids (with or without acetaminophen) for non-CIPN pain, up to 4 daily doses will be allowed during the study, with daily recording of analgesic consumption. The total amount of acetaminophen (from opioid-acetaminophen combination and PRN acetaminophen alone) will not exceed 4 grams/day. In subjects with liver disease (AST or ALT increased, but less than 3 times the upper normal level), the total daily dose of acetaminophen will be limited to 2 grams. Based on these considerations, each patient will receive individual written instructions regarding PRN analgesic use, and will be required to report it appropriately.

Outcomes Assessment:

Clinical Efficacy

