2.4.9. Dealing with missing data

If less than 10% data on primary outcomes are missing, we will perform our primary analysis per protocol, and perform sensitivity analysis using intent to treat (ITT) approach, where missing pain intensity data will be imputed using last observation carried forward (LOCF) method. If more than 10% primary outcomes data are missing, we will use mixed-effects model imputation method [full information maximum likelihood (Little, D'Agostino et al. 2012)], which considers the reasons for missingness, and is more appropriate for reducing bias.

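### Several withdrawal rules end pain data collection as well as study drug, so the day 24-28 outcome may be missing for reasons tied to treatment and pain

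*Combined protocol and SAP*

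**What the plan says.** Three triggers remove a subject from the study:

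- **Grade 3 or higher.** Section 3.2: "Subjects will be withdrawn if they experience any Grade 3 or higher adverse effect". Section 2.4.3 says that any CTCAE event of at least "grade 3 will trigger subject withdrawal from the study".
- **More analgesia.** Section 3.2: "Subjects will be withdrawn from the study if they require an increase in their other analgesic drugs, including chronic around-the-clock opioid dose".
- **PRN opioid.** Section 3.2 also withdraws subjects who "need more than 4 PRN daily doses of a short-acting opioid".

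Two routes do not end participation. Section 2.4.3 (Rescue Analgesia) states: "Study subjects will be allowed to take oral acetaminophen (paracetamol) as rescue analgesic". And under Section 3.2 a subject who chooses to stop treatment in period 1 may either leave or elect "to continue the second phase of the study after a 2 week washout period".

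The primary outcome uses diary pain on days 24-28 of each period (Sections 2.4.3 and 2.4.7). No section provides for diary entries after withdrawal.

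Section 2.4.9 covers missing data: "If less than 10% data on primary outcomes are missing, we will perform our primary analysis per protocol", with an intent-to-treat LOCF analysis as sensitivity. Above 10% it switches to a mixed-effects, full information maximum likelihood method. Section 2.4.7 gives the paired mean comparison and the 50% responder comparison no rule of their own for withdrawn subjects.

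**The concern.** A subject withdrawn before day 24 has no outcome for that period. One withdrawn in period 1 also has none for period 2. In either case there is no within-subject contrast.

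The triggers are not obviously neutral. Needing more of another analgesic is close to being a poor pain outcome. Adverse events plausibly follow the active drug: Section 2.1 cites an NNH of 13.9 for adverse-effect dropout on pregabalin. Outcomes may therefore be missing in a way that depends on treatment and on the pain score that would have been recorded.

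At stake are the slope comparison when it is run per protocol, the paired mean comparison and the responder proportions with the NNT. The likelihood method is exposed too if the pain and rescue data recorded before exit do not account for the withdrawals.

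**Working it through.** **1. The plan's own figures (Section 2.4.8).** Inputs: difference 0.3, SD 0.5, alpha 0.05, power 85%. A two-sided paired t-test on the within-subject difference (noncentral t) gives n = 27 with power 85.1%, matching the plan. Dropout: 27 / (1 - 0.20) = 33.75, so 34; the plan recruits 35. At 20% dropout, 35 x 0.20 = 7 are lost and 28 complete.

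**2. Which analysis would be primary (Section 2.4.9).** Count each lost subject as missing. Then 3/35 = 8.6% keeps the per-protocol analysis and 4/35 = 11.4% triggers the likelihood method. With 20% dropout, P(at least 4 of 35 lost) = 0.94 (binomial). The plan's own assumption therefore points to the likelihood method. The unit of the 10% is not stated. Counted over 70 subject-periods, 7 losses all in period 2 give 7/70 = exactly 10%, which neither branch covers; 7 losses all in period 1 give 14/70 = 20%.

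**3. Scale of the adverse-effect route.** 35 / 13.9 = 2.5 extra adverse-effect dropouts over one pregabalin period, if the cited NNH carried over to CIPN and to these rules. That is an assumption. It shows only that treatment-related loss is plausible.

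**4. Effect on completers.** The documents give no withdrawal rates by reason, so this is illustration only. Assumptions: true standardised slope difference -0.30 (placebo slope 0 or -0.1), true mean difference 0.40 SD, within-subject residual correlation 0.4, logistic withdrawal with strength 1 or 2 per SD of response, 1,000,000 simulated subjects.

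| Withdrawal depends on | Slope difference, 9% lost | Slope difference, 20% lost | Mean difference, 20% lost |
|---|---|---|---|
| Nothing about response | -0.30 | -0.30 | 0.40 |
| High response on pregabalin | -0.27 to -0.29 | -0.25 to -0.28 | 0.24 to 0.30 |
| Low response on pregabalin | -0.27 to -0.29 | -0.25 to -0.28 | 0.50 to 0.56 |
| Low response in either period | -0.29 to -0.30 | -0.28 to -0.29 | 0.36 to 0.38 |

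The slope difference shrinks by 0-10% at 9% withdrawal and 0-16% at 20%. The mean difference moves in both directions.

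A variant removes the worst 10% on placebo and nobody on pregabalin (correlation 0.5). The mean difference falls by about 0.10 SD. The slope difference stays at -0.30 if the placebo slope is 0, but becomes -0.33 (about 10% larger) if it is -0.2. Shrinkage is therefore not guaranteed.

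**5. Power.** With 28 completers and SD 0.5 held fixed, power is 86.4% at 0.30, 78.7% at 0.27 and 72.3% at 0.25.

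**The case against.** The strongest reply has five parts.

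- **The primary analysis is a slope comparison.** Section 2.4.7 says it does not depend on the average difference between treatments, and losing poor placebo responders need not move it. This stands: in the placebo-only variant with zero placebo slope it did not move.
- **A completer primary is unlikely at the plan's own dropout rate.** This stands. It does not settle the matter, because the likelihood method is valid only if withdrawal is explained by the data modelled. Daily pain and rescue use are recorded up to exit, so that may be reasonable. But Section 2.4.9 specifies no model, and its remark that the method takes account of the reasons for missingness names no way of doing so. Adequacy is uncertain, not refuted.
- **The triggers are narrower than any need for pain relief.** This stands. Acetaminophen rescue is allowed, and grade 2 events lead to dose reduction.
- **The 20% dropout covers all causes**, including surgery, chemotherapy and subject choice. This stands, so 7 of 35 does not size these triggers.
- **In a pilot study of predictors of drug response, pain after stopping drug answers a different question.** This stands in part, and is why results with and without those days are needed.

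A reader might infer that the completer analysis is biased, by a known amount. One tempting calculation removes the worst 10% on placebo: the placebo mean rises by 0.195 SD, half of that is 0.0975 SD at correlation 0.5, and an assumed SD of 25-35 points turns it into 2.4-3.4 points of percent pain reduction. The documents do not support using that figure. The planned paired test is on absolute reduction, the SD is assumed, and the scenario ignores losses on pregabalin, which can offset or reverse the shift.

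**Conclusion.** The point holds as a design weakness that creates a risk of informative missingness. The rules end study participation, and with it the diary, for reasons plausibly related to treatment and pain, and the missing-data plan does not clearly repair this.

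Neither size nor direction can be derived from the documents. Under the assumed logistic models the slope difference shrinks by roughly 0-16%, the placebo-only variant can enlarge it, and the mean contrast can move either way. Withdrawal unrelated to response gave no bias. It would therefore go too far to say that the results are biased, or that they favour one treatment.

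Two inconsistencies also need reconciling. Subjects who choose to stop in period 1 may enter period 2, while the withdrawal rules give other subjects no such route. And Section 2.4.3 speaks of any CTCAE event, Section 3.2 of an adverse effect.

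**What to change.** Leave all stopping rules as they are, and separate stopping study drug from stopping data collection.

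1. Unless consent is withdrawn, continue the daily smartphone pain and rescue diary to day 28 of that period.
2. Use those data in an analysis of all randomised subjects, reported with and without the days after stopping.
3. In the 50% comparison, count subjects who stopped for adverse effects or more analgesia as non-responders for that period.
4. Add a missing-not-at-random sensitivity analysis.
5. Reconcile who may enter period 2 after stopping in period 1, and the grade 3 wording of Sections 2.4.3 and 3.2.

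The cost is protocol wording, plus the phone staying with the subject for up to 4 more weeks; the phones and prompts are already in place (Section 2.4.3, Electronic data collection). There are limits. Pain after stopping partly reflects other analgesics. The non-responder rule will include some events unrelated to pain or drug. A missing period 2 is not recovered, so the within-subject contrast stays incomplete for those subjects.

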3.3 Potential Risks

3.3.1 Potential risks from pregabalin

Potential adverse effects usually associated with pregabalin include dizziness, somnolence, xerostomia, headache, visual disturbances, peripheral edema and abnormal gait (all less than 15% prevalence).

Other common (>10% prevalence) adverse effects may include fatigue, ataxia, tremor and weight gain. Less common (5-10% prevalence) adverse effects reported with pregabalin include abnormal thinking, confusion, euphoria, speech disorder, pain, insomnia and constipation. Rare but potentially serious adverse effects reported with pregabalin use are: angioedema, suicidal thoughts, allergic reaction, infection, hypertension, hypotension, amnesia, hypoglycemia, vomiting, thrombocytopenia, and nystagmus.

Subjects will be educated regarding the possible adverse effects, and these will be monitored through weekly screening of patient-reported diary and weekly telephone follow-ups with the patient.

3.3.2 Potential risks from thermal testing

Risk of injury related to thermal pain testing is minimal. Thermal testing is widely used and safe. While thermal testing does produce pain, risks to the individual are minimal, because 1) the pain is transient in nature and generally subsides immediately after the procedure; 2) subjects are instructed that they may stop any procedure at any time with no adverse consequences; and 3) the level of pain experienced by subjects is below their tolerance level. With thermal stimulation there is a very slight risk of a burn, but this is minimized by the following: 1) positive lockout of stimulus parameters above 50°C; and 2) the stimulator has built in a shut-down system to prevent the delivery of prolonged or high intensity stimuli. Both TSA-II and Q-Sense have FDA 501(k) clearance (K922052).

3.3.3 Potential risks from skin biopsy

Potential risks associated with 3-mm skin punch biopsy include local pain, infection, and minor bleeding. The pain is transient in nature, and local infiltration with lidocaine typically eliminates the pain. The procedure is performed by a trained health care professional using aseptic technique with sterile skin biopsy kit to minimize the risk of infection. Subjects will be educated regarding the possible risks, and are informed that providing a skin biopsy is voluntary, and refusal will not affect their participation in the study.

3.3.4 Other Potential Risks

No psychological risks to subjects are envisioned. Subjects may experience a loss of confidentiality. Investigators will keep subjects' participation confidential to the extent permitted by law. However, it is possible that others may become aware of subjects' participation in this study and may inspect and copy records pertaining to this research. Some of these records could contain information that personally identifies subjects.

3.4 Procedures to Minimize Potential Risks

Studies are conducted in the Washington University Clinical Research Center under the supervision of the PI and the co-investigator. The PI is trained and experienced in performing research in human subjects. The co-investigator is board certified oncologist with extensive experience in managing cancer patients.

Inclusion and exclusion criteria, monitoring, and the clinical protocol are designed to ensure that risks are minimal. Subjects are informed that participation is voluntary and they may refuse to participate and may withdraw from the study at any time without penalty. A pregnancy test will be performed on women of childbearing potential and subjects excluded if pregnant. Subjects will be told that in the event of a physical injury as the direct result of study procedures, they will be cared for by a member of the investigating team at no cost, within the limits of the Washington University compensation plan.

With regard to confidentiality; 1) all subjects will be assigned a study ID number, 2) Samples will be kept confidentially. They will be coded, with a key to the code linking code numbers to names kept at a separate location, under lock and key. 3) The link to identifiers will be destroyed at the end of the study. 4) Data will be stored under lock and key (office, file cabinet) and only the investigators and research team will have access. If data are published, there will be no link to identifiers. Study data will not be revealed to any organization, individuals other than the subjects, or the subjects themselves. 5) Study data will not be entered in subjects' medical records

3.5 Data and Safety Monitoring Plan

In compliance with the Washington University Institutional Data and Safety Monitoring Plan, the Principal Investigator will provide a Data and Safety Monitoring (DSM) report to the Washington University Quality Assurance and Safety Monitoring Committee (QASMC) semi-annually beginning six months after accrual has opened (if at least five patients have been enrolled) or one year after accrual has opened (if fewer than five patients have been enrolled at the six-month mark).

The Principal Investigator will review all patient data at least every six months, and provide a semi-annual report to the QASMC. This report will include:

- HRPO protocol number, protocol title, Principal Investigator name, data coordinator name, regulatory coordinator name, and statistician
- Date of initial HRPO approval, date of most recent consent HRPO approval/revision, date of HRPO expiration, date of most recent QA audit, study status, and phase of study
- History of study including summary of substantive amendments; summary of accrual suspensions including start/stop dates and reason; and summary of protocol exceptions, error, or breach of confidentiality including start/stop dates and reason
- Study-wide target accrual and study-wide actual accrual
- Protocol activation date
- Average rate of accrual observed in year 1, year 2, and subsequent years
- Expected accrual end date
- Objectives of protocol with supporting data and list the number of participants who have met each objective
- Measures of efficacy
- Early stopping rules with supporting data and list the number of participants who have met the early stopping rules
- Summary of toxicities
- Abstract submissions/publications
- Summary of any recent literature that may affect the safety or ethics of the study

The study principal investigator and Research Patient Coordinator will monitor for serious toxicities on an ongoing basis. Once the principal investigator or Research Patient Coordinator becomes aware of an adverse event, the AE will be reported to the HRPO and QASMC according to institutional guidelines.

4. HUMAN SUBJECTS RESEARCH

4.1 Protection of Human Subjects

The study will be conducted under appropriate Washington University Institutional Review Board protocols and consent forms approvals. The study will be conducted under the supervision of the PI, a GCP-certified pharmacist with several years of experience in the conduct of human studies, and co-PI, a board-certified oncologist with extensive clinical and human research experience.

4.2 Sources of Materials

Subjects will be recruited from Outpatient Clinics of Siteman Cancer Center and Washington University Pain Management Center.

Data on comorbidities and concomitant medication use are provided by subjects as well as retrieval of medical records. Specimens include blood obtained for determining kidney and liver function for study eligibility, and for determining pregabalin plasma concentration. Urine specimen will be obtained from women of childbearing potential for a pregnancy test. Skin biopsy specimen (optional) is obtained from the foot for determining small nerve fiber density in the skin. Other data including baseline quantitative sensory testing are obtained exclusively for research purposes.

4.3 Recruitment and Informed Consent

Participants will be recruited primarily through Siteman Cancer Center and Washington University Pain Management Center, referred by the corresponding physicians. In addition, we will post flyers and recruit participants through Volunteers for Health organization. Interested subjects will contact the investigators. Subjects will be given verbal (initially) and then written descriptions of the study aims, procedures, risks, and benefits, and will be required to give written informed consent. A member of the investigative team provides all study descriptions, informed consent, and answers all questions. Placebo administration is a part of the study, and the subjects will be informed that they will be receiving placebo at one of their study periods. Subjects are informed verbally and in writing that participation is voluntary and they may refuse to participate and may withdraw from the study at any time without penalty.

4.4 Potential Benefits of the Proposed Research to the Subjects and Others

The potential benefit to the study subjects is a relief of their chronic pain associated with CIPN. There are limited data suggesting that pregabalin may be effective in this group of patients. Potential understanding of which patients are more likely to respond to pregabalin may lead to improved patient outcomes from which the study subjects and other subjects suffering from painful CIPN may potentially benefit in the future. The society may benefit from a new approach of optimizing treatment of neuropathic pain.

